Study Protocol with Statistical Analysis Plan and Informed Consent Form

Title	Details
Date	6 May 2024
NCT Number	NCT05163964
Study title	Chronotype, Chrononutrition and Glucose Tolerance Among Prediabetic Individuals: Chrono-DM™
Name and Institution of Principal Investigator	[name] [name] Department of Bioscience Faculty of Applied Sciences (FOAS) Tunku Abdul Rahman University Management and Technology (TARUMT) [contact]
Name and Institution of Co-Researchers	[name] [name] Assistant [name] of Food Science and Nutrition UCSI University, Malaysia [contact] [name] [name] Assistant [name] of Reproductive Medicine Duke-NUS Medical School, Singapore [contact] [name] [name] Deputy Dean Faculty of Applied Sciences Tunku Abdul Rahman University Management and Technology (TARUMT) [contact] [name] A/L [name] Physician Department of Emergency and Trauma Hospital Serdang, Malaysia [contact] [name]. [name] Professor, Deputy Dean of Graduate School, Lecturer Faculty of Health Sciences Universiti Kebangsaan Malaysia [contact]
Sub investigators at the site and Co-Researchers	[name] [name] Family Specialist Community Clinic Batu Berendam, [contact]

	
[name] [name] Medical Officer Community Clinic Batu Berendam [contact]
 
[name] Clinical/ Community Dietitian Community Clinic Kuala Sungai Baru Ministry of Health [contact]

Principal investigators at the site and Name of PhD Student	
[name] Department of Bioscience Faculty of Applied Sciences (FOAS) Tunku Abdul Rahman University Management and Technology (TARUMT) [contact]

Study Population	Prediabetic individuals in Community Clinic Melaka
Study Design	
Study Type: Prospective Longitudinal Study Sampling Method: Convenient sampling method

General Objective	To determine the associations of chronotype and chrononutrition with glucose tolerance among prediabetic individuals in Malaysia.
Specific Objectives	
 1) To investigate the effect of chrononutrition on glycemia measures among prediabetic individuals. 2) To investigate the associations of lifestyle factors with glycemia measures among prediabetic individuals. 3) To investigate the associations of anthropometric measurements with glycemia measures among prediabetic individuals.

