Study outcomes	
The main outcomes of this study are
 
 1) The change of baseline glycated hemoglobin (HbA1c) among prediabetes adults at 6 months. 2) The change of baseline fasting plasma glucose (FPG) among prediabetes adults at 6 months. 3) The change of baseline 2-hour post-load plasma glucose among prediabetes adults at 6 months. 4) The change of baseline continuous glucose monitoring (CGM) profile among prediabetes adults at 6 months. 
Secondary outcome of this study are
 
 1) The change of eating misalignment among prediabetes adults at 6 months. 2) The change of chronotype among prediabetes adults at 6 months.
Sample Size	120 prediabetic individuals
Study Duration	1 March 2022 until 31 December 2023
Name and Address of Sponsor	Fundamental Research Grant Scheme (FRGS), Ministry of Higher Education/ UMalaya (FRGS/1/2021/SKK06/TARUC/02/1)

Ethics Approval	Tunku Abdul Rahman University Management and Technology Ethics Committee (TAR UC/EC/2021/02-3) Medical Research and Ethics Committee (RSCH ID-21-00114-IVI)
-----------------	---

Executive Summary:

Early meal timing affects the circadian rhythmicity and influenced the postprandial blood glucose level in response to meal in diabetes patients. In the other words, diabetes patients with earlier meal timing had a stable glycemic control compared with those with late meal timing. This is a new concept to switch the meal timing earlier than later in diabetes self-monitoring management. However, there is insufficient evidence from Southeast Asia to determine the optimal-meal-timing and its association with glycemic measures in prediabetes individuals. Hence, this study carried out to determine the associations of chronotype and chrononutrition with glucose tolerance among prediabetic individuals in Malaysia.

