3. RESEARCH METHODOLOGY

Hypothesis:

The morning chronotype and early meal-timing are associated with low glycemic outcome among prediabetic individuals.

Research Questions:

Is the morning chronotype and early meal-timing are associated with better glucose tolerance among prediabetic individuals?

General objective:

To determine the associations of chronotype and chrononutrition with glucose tolerance among prediabetic individuals in Malaysia.

Specific objectives:

1. To examine the associations among chronotype, chrononutrition and glucose outcomes.
2. To investigate the association between lifestyle factors (physical activity level, light exposure, diet timing, sleep pattern) and chrononutrition.
3. To investigate the association between anthropometry measurements and glycemic outcomes.

Description of Methodology:

Participants will be recruited using the convenience sampling method. The proposed study will be conducted in community clinics in Malacca, Malaysia. Malacca is the capital of the coastal state, located in southwestern Malaysia, with an estimated total population of 0.93 million in the year 2019 (Department of Survey and Mapping Malaysia, 2021). In 2019, National Health and Morbidity Survey reported that 17% of Malaccan adults had hyperglycemia and 13.7% of them had known diabetes. Malacca is 1 out of the top five states showing the highest prevalence of diabetes in Malaysia (IPH, NIH and MOH, 2019). Permission to carry out data collection has been granted by the Medical Research and Ethics Committee (MREC) (RSCH ID-21-00114-IVI). The study protocol has been reviewed and approved by the Tunku Abdul Rahman University College (TARUC) research ethics committee (TAR UC/EC/2021/02-3).

During the process of recruitment, a trained research assistant (one of the co-researcher), clinical dietitian (one of the co-researcher) or family medicine specialist

(one of the co-researcher) will inform potential prediabetic individuals research protocol verbally and written information will be provided. Newly diagnosed prediabetic individuals who are agreeable to participate will provide written informed consent. Baseline and follow up appointments will be determined based on the community clinic appointment schedules. Those who decline to participate will continue to receive their routine treatment as usual, and care provided to each prediabetic individual will not be affected by the decision to either participate or not participate in the study.

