Anthropometric measurements (Appendix J) will be measured at the first, second and third visit. Body weight, body fat percentage and visceral fat of each participant will be measured twice using a body fat analyzer (HBF-375, Karada) and recorded to the nearest 0.1 kg, 0.1 % and 1 unit, respectively. Participants will be weighted with their minimal cloths on, barefoot, without belt and emptied pockets. They will be asked to stand still with the body weight equally distributed on both feet. Participants have to be in the Frankfurt plane, where the body is upright, upper limbs are at the body's sides with the palms facing forward, feet flat and directed forward, directly facing the researcher assistant. The height of each participant will be measured twice using a SECA portable stadiometer Model 217 (SECA GmbH & Co., Hamburg, Germany) attached to a smooth wall and recorded to the nearest 0.1 cm. Participants will be asked to stand erect, in their bare feet, with their heels, buttocks, head and shoulder blades in a vertical line against the wall. Height will be measured in the upright position against a vertical scare and with the head positioned so that the top of the external auditory meatus is in the level with the inferior margin of the bone orbit. Waist and hip circumferences of the respondents will be measured twice, according to the standardized protocol by the WHO (2008). Waist circumference will be measured at the approximate midpoint between the lower margin of the last palpable rib and the top of the iliac crest. Hip circumference will be measured around the widest portion of the buttocks, with the tape parallel to the floor. For both measurements, the participants should stand with feet close together, arms at the side and body weight evenly distributed, and should wear little clothing. Both waist and hip circumferences will be measured to the nearest 0.1 cm by using a Lufkin tape model W606PM (Apex Tool Group, Sparks, MD, USA). The reported measurements are the average values from both readings.

Study Outcomes

The main outcome of the study is the glycemic outcome including FPG (mmol/L), 2hPPG (mmol/L), HbA1c (%), and glucose variability from CGMS. The secondary outcomes are chronotype from the validated questionnaire MCTQ, and chrononutrition from the validated questionnaire CPQ, 3 days dietary record, anthropometry measurements, physical activity level from the validated questionnaire IPAQ, sleep

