pattern from the validated questionnaires PSIQ and light exposure from the validated questionnaire HLEQ.

Statistical Analysis

All data will be performed statistical analysis using the SPSS software version 20 (SPSS Inc., Chicago, IL, USA). The socio-demographic will be presented as mean, standard deviations, median, interquartile range, frequency, and percentage. Data cleaning will be performed to exclude the outlier data before the normality is checked using Kolmogorov-Smirnov Test. The investigator considered $p < 0.05$ to be statistically significant. Chronotype, sleep quality, and light exposure will be analyzed as categorical variables whereas dietary intake, chrononutrition, anthropometry, glycemic measure, and physical activity will be analyzed as continuous variables.

The investigator will perform a multivariable generalized linear model to examine the association between night meal pattern (last night mealtime either dinner or supper with calories intake, frequency of night snacking, and the total number of the night snacking) and glycemic outcome (HbA1c, FPG, 2hPPG, CGM profile) by adjusting for the potential covariates. Specifically, nighttime will be characterized by the time range from 1900 and 0659 hours based on Malaysia solar time. The investigator will explore the late-night meal timing in 2000, 2100, and 2200 to examine its association with glycemic outcomes. The potential confounders include sociodemographic characteristics, physical activity, sleep pattern, sedentary behavior, diet quality, and light exposure will be controlled. ANCOVA test will be performed to understand the association between chrononutrition (breakfast skipping, meal frequency, eating window, sleep timing, chronotype, and fasting pattern) with glycemic variables, controlling for potential covariates (sociodemographic characteristics, light exposure, diet quality, physical activity and sleep pattern).

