To investigate the association of physical activity (MET score and steps count), sedentary behaviors (MET score), sleep pattern (sleep duration), diet quality (distribution of total energy, carbohydrate, protein, and fat), and light exposure (timing responded to a different type of light) with glycemic outcome, the multivariable generalized linear model will be conducted. Meanwhile, anthropometric measures (body mass index, body fat, and waist circumference) will be categorized as either normal or overweight and obesity group, followed by using logistic regression to examine the association between anthropometry status and glycemic outcome (non-diabetes or diabetes). In addition, the glycemic outcome will be categorized into diabetes incidence (diabetes and non-diabetes) to determine the participants who had been diagnosed with diabetes at 6 months. A logistic regression test will be used to examine the association between early and late-night mealtime and diabetes incidence.

Quality control

To ensure that the database accurately reflects the data reported in the questionnaires, a pre-test will be carried out. The research assistant trained to conduct the study procedures included interviewing administrative questionnaires, CGMS device, 3 days dietary record, and pedometer. Monthly meetings are held with the principal

investigator to review study procedures and progression. A monthly report will be documented after the meeting.

Data monitoring and management

Participants are anonymized and assigned with a specific ID at study entry. To ensure accuracy and completeness of data entry, data are checked by identifying if there is any outlier or missing value. The data checking process is performed in the first, third and sixth month of the data collection, such that the experience gained can be used to train the research assistant for improvement. Paper documents are kept in a locked cabinet and electronic data are stored on password-protected computers which can only be accessed by research team members. All records will be kept for at least 5 years after completing the study. After 5 years, all papers will be shredded using an office shredder. Extra care should be taken with sensitive or confidential information and a secure paper destruction service bin used. Digital data will be destroyed by deleting or overwriting information and destroying the physical media, such as CD rom.

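### Objective 3 has no planned model linking anthropometry to any main glycaemic outcome; its only analysis is a logistic regression of diabetes yes/no on weight category

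*Combined protocol and SAP*

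**What the plan says.** The synopsis gives objective 3 as "To investigate the associations of anthropometric measurements with glycemia measures among prediabetic individuals". Section 3, Specific objectives, words it as "To investigate the association between anthropometry measurements and glycemic outcomes". Neither limits the outcome to a diagnosis of diabetes.

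The synopsis defines the main outcomes as changes over six months, the first being "The change of baseline glycated hemoglobin (HbA1c) among prediabetes adults at 6 months"; fasting glucose, 2-hour glucose and the CGM profile follow. Section 3, Study Outcomes, agrees on the variables: "The main outcome of the study is the glycemic outcome including FPG (mmol/L), 2hPPG (mmol/L), HbA1c (%), and glucose variability from CGMS".

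Section 3, Statistical Analysis, first sets a general rule: "dietary intake, chrononutrition, anthropometry, glycemic measure, and physical activity will be analyzed as continuous variables". It then assigns models by exposure:

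- Night meal pattern: generalized linear model on HbA1c, fasting glucose, 2-hour glucose and CGM.
- Chronotype and the other chrononutrition variables: ANCOVA on glycaemic variables.
- Physical activity, sedentary behaviour, sleep, diet quality and light: for the glycaemic outcome, "the multivariable generalized linear model will be conducted".
- Anthropometry: the three measures are dichotomised, "followed by using logistic regression to examine the association between anthropometry status and glycemic outcome (non-diabetes or diabetes".

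On timing, "Anthropometric measurements (Appendix J) will be measured at the first, second and third visit". The analysis text does not say which visit supplies the exposure.

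**The concern.** Followed as written, the plan answers objective 3 only through a diagnosis. HbA1c, fasting glucose and 2-hour glucose would count only insofar as they help to establish that diagnosis, and CGM not at all, because none of the diagnostic tables in section 3 uses it. The exposure side is cut to two groups as well.

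The diagnosis may also be uncommon at six months. An odds ratio resting on a handful of cases would be very imprecise, or not estimable if one weight group has none. A null result could then be misread as showing that anthropometry is unrelated to glycaemia, while the continuous data that bear on the question go unused.

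**Working it through.** **Textual check.** I went through every model in Statistical Analysis. Anthropometry is not an exposure in the night-meal model, the ANCOVA or the lifestyle model, and is not named in the covariate lists given there. The schedule in section 4 mentions associations between the variables but gives no model. The logistic regression is therefore the only analysis that names anthropometry. This finding needs no assumption.

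**The plan's own sample size.** Sample size Calculation uses a linear regression t test for one coefficient: effect size 0.13, two-sided alpha 0.05, power 0.90, result 83. Entering 0.13 as f² gives noncentrality √(83 × 0.13) = 3.28 and power 0.90, so 83 reproduces, and 83/(1 − 0.5) = 166. If 0.13 were a partial correlation, f² = 0.0169/0.9831 = 0.0172 and power at 83 would be 22%. The input concerns chrononutrition and a continuous outcome, so the calculation does not support the logistic regression, nor does it establish power for a continuous anthropometry model.

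**How many cases?** Section 2, 1.1 Prediabetes, cites 5.8% to 18.3% progressing per year without appropriate interventions. Assume a constant hazard over six months:

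- 1 − (1 − 0.058)^0.5 = 0.0294, and 83 × 0.0294 = 2.4 cases
- 1 − (1 − 0.183)^0.5 = 0.0961, and 83 × 0.0961 = 8.0 cases

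I use 83 completers because that is what 166 recruits leave after the planned 50% dropout.

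**Precision of the planned model.** Further assumptions: odds ratio 3, groups of 42 and 41, no covariates, overall rate held fixed. Power is by exact enumeration of two binomials with the likelihood-ratio test.

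| | Rate 2.9% | Rate 9.6% |
|---|---|---|
| Expected cases, overweight/obese and normal | 1.8 and 0.6 | 5.9 and 2.1 |
| Power | 16% | 33% |
| P(no case), overweight/obese and normal | 0.154 and 0.539 | 0.002 and 0.115 |
| P(at least one group without a case) | 61% | 12% |
| SE of log odds ratio | 1.492 | 0.836 |
| Approximate 95% CI, 3 × exp(±1.96 SE) | 0.16 to 56 | 0.58 to 15 |

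The fourth row is the sum of the two probabilities minus their product, for example 0.154 + 0.539 − 0.083 = 0.610. The test's actual type I error is about 7% at both rates, so the power figures are slightly flattering. At an assumed rate of 20%, power is about 50% and the empty-group risk is under 1%.

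**Cost of cutting both sides.** Assume one normal exposure and one normal outcome with correlation 0.30, unadjusted, N = 83, exposure split at the median. Both continuous: f² = 0.09/0.91 = 0.0989, noncentrality √(83 × 0.0989) = 2.87, power 81%. Both cut: 17% with 2.9% cases, 28% with 9.6% and 36% with 20%.

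**The case against.** The strongest reply is that a specific statement overrides a general one. Statistical Analysis says plainly that the three measures will be categorised, so a reader who infers a flat contradiction goes too far: it can be an unlabelled exception. That stands. It does not supply an analysis of objective 3 on any main outcome.

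A reader might also infer that diabetes status is nothing more than thresholded HbA1c, fasting glucose and 2-hour glucose. The documents do not support this. The diagnostic criteria in section 3 also use random glucose, symptoms and repeat testing, and the plan speaks of a diagnosis at six months. Progression to diabetes also motivates the study in section 1. The logistic regression therefore answers a question of its own and should stay.

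The magnitudes rest on assumed rates, odds ratio and split. Routine care could lower the rate, and the true rate could also be higher. The continuous-versus-cut comparison is unadjusted, so it does not measure the gain from a baseline-adjusted model. The hypothesis and sample size concern chronotype and meal timing, which limits how much weight objective 3 carries. All of this stands, but none of it touches the gap in the text.

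**Conclusion.** The concern holds as a gap in the analysis plan. One of three specific objectives has no model on any main outcome as defined, the relation between the general rule and the categorised analysis is unexplained, and the exposure visit is not stated.

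The size is illustrative. With 83 completers and the assumptions above, the planned model would rest on roughly 2 to 8 cases, and its power would be well below the 90% used for the study's linear model. If the synopsis figure of 120 were recruited with the same dropout, 60 would complete and 1.8 to 5.8 cases would be expected.

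Two further inferences are not supported. The 90% figure does not carry over to a continuous anthropometry model. Nor does this point, which concerns objective 3, call for any change to the separate logistic regression of mealtime on diabetes incidence.

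**What to change.** 1. In Statistical Analysis, reconcile the continuous-variable rule with the categorised analysis, and name the visit that supplies the anthropometric exposure.
2. Add for objective 3 the generalized linear model already used for night meal pattern and lifestyle exposures: continuous baseline BMI, body fat and waist circumference, one per model, against 6-month HbA1c, fasting glucose and 2-hour glucose. Adjust each outcome for its own baseline value, in line with the synopsis outcomes, and list the covariates. Report slopes with 95% confidence intervals.
3. Add CGM at the visit or visits where it is actually measured, after reconciling three places: the synopsis (change from baseline at six months), the methodology (sensor worn from the second visit) and section 4 (devices distributed at baseline and at the second visit).
4. State the number of pairs tested: 3 × 3 = 9, plus 3 for each CGM metric. With one metric that is 12, and 12 × 0.05 = 0.6 would be expected to reach p < 0.05 by chance if no association were real.
5. Keep the anthropometry logistic regression as a supporting analysis of diagnosed diabetes, with n/N by group and a sparse-data method such as Firth's if cases are few.

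The cost is SAP wording and a few more models and tests, with no new data. The document is dated 6 May 2024 and section 4 schedules third visits to end on 06/03/2024, so the added models should be labelled as specified after data collection if the last visits were complete.
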